6.1.3 Permitted Concomitant Medications and Procedures (*if applicable*)

CONFIDENTIAL

This document is confidential. Do not disclose or use except as authorized.

The following medications and procedures are permitted during the study:

- Antiemetics, including 5-HT₃ serotonin receptor antagonists, may be used at the discretion of the investigator.
- Loperamide or other antidiarrheal should be used for symptomatic diarrhea at discretion of the investigator. The dose and regimen will be according to institutional guidelines. IVF should be given to prevent volume depletion.
- Growth factors (eg, granulocyte colony stimulating factor [G-CSF], granulocyte macrophage-colony stimulating factor [GM-CSF], recombinant erythropoietin) are permitted. Their use should follow published guidelines and/or institutional practice;. Erythropoietin will be allowed in this study. Their use should follow published guidelines and/or institutional practice.
- **Patients should be transfused with red cells and platelets as clinically indicated and according to institutional guidelines.** Patients should not have a CBC drawn to confirm eligibility or for on-treatment decisions (see section 6.2.1.1: Dose Reductions for Hematologic Toxicities) less than 3 days following a platelet transfusion. Patients MUST HAVE a CBC drawn to confirm eligibility or for on-treatment decisions (see section 6.2.1.1: Dose Reductions for Hematologic Toxicities) more than 3 days following a platelet transfusion. If a patient receives a platelet transfusion, then a 3-day wait is recommended for the CBC draw that would either confirm eligibility or guide the decision with regards to the next dose (drug hold/dose reduce per Section 6.2.1.1).
- Antiviral therapy such as acyclovir may be administered if medically appropriate.
- Concomitant treatment with bisphosphonates will be permitted, as appropriate.
- Patients who experience worsening neuropathy from baseline may be observed for recovery, and have dose reductions/delays as indicated in the protocol, and any supportive therapy or intervention may be initiated as appropriate at the discretion of the investigator.
- Supportive measures consistent with optimal patient care may be given throughout the study.

6.1.4 Precautions and Restrictions

- **Fluid deficit should be corrected before initiation of treatment and during treatment.**
- **Nonsteroidal anti-inflammatory drugs (NSAIDs) should be avoided with impaired renal function given reported NSAID-induced renal failure in patients with decreased renal function.**

Pregnancy

It is not known what effects ixazomib has on human pregnancy or development of the embryo or fetus. Therefore, female patients participating in this study should avoid becoming pregnant, and male patients should avoid impregnating a female partner.

CONFIDENTIAL

This document is confidential. Do not disclose or use except as authorized.

Nonsterilized female patients of reproductive age group and male patients should use effective methods of contraception through defined periods during and after study treatment as specified below.

Female patients must meet 1 of the following:

- **Postmenopausal for at least 1 year before the screening visit, or**
- **Surgically sterile, or**
- **If they are of childbearing potential, agree to practice 2 effective methods of contraception from the time of signing of the informed consent form through 90 days after the last dose of study drug, or**
- **Agree to practice true abstinence, when this is in line with the preferred and usual lifestyle of the subject. (Periodic abstinence [eg, calendar, ovulation, symptothermal, postovulation methods] and withdrawal are not acceptable methods of contraception.)**

Male patients, even if surgically sterilized (ie, status postvasectomy) must agree to 1 of the following:

- **Practice effective barrier contraception during the entire study treatment period and through 90 days after the last dose of study drug, or**
- **Agree to practice true abstinence, when this is in line with the preferred and usual lifestyle of the subject. (Periodic abstinence [eg, calendar, ovulation, symptothermal, postovulation methods for the female partner] and withdrawal are not acceptable methods of contraception.)**

6.1.5 Management of Clinical Events (*if applicable*)

Adverse drug reactions such as thrombocytopenia, diarrhea, fatigue, nausea, vomiting, and rash have been associated with ixazomib treatment. Management guidelines regarding these events are outlined below. Further details of management of ixazomib AEs are described in Section 6 of the ixazomib IB.

Prophylaxis Against Risk of Reactivation of Herpes Infection

Patients may be at an increased risk of infection including reactivation of herpes zoster and herpes simplex viruses. Antiviral therapy such as acyclovir, valacyclovir, or other antivirals may be initiated as clinically indicated. Other antivirals are also acceptable.

Nausea and/or Vomiting

Standard anti-emetics, including 5-HT₃ antagonists, are recommended for emesis occurring upon treatment initiation; prophylactic anti-emetics may also be considered. Dexamethasone should not be administered as an anti-emetic. Fluid deficit should be corrected before initiation of study drug and during treatment.

CONFIDENTIAL

This document is confidential. Do not disclose or use except as authorized.

Diarrhea

Prophylactic antidiarrheals will not be used in this protocol. However, diarrhea should be managed according to clinical practice, including the administration of antidiarrheals once infectious causes are excluded. Fluid intake should be maintained to avoid dehydration. Fluid deficit should be corrected before initiation of treatment and during treatment.

Erythematous Rash With or Without Pruritus

As with bortezomib, rash with or without pruritus has been reported with ixazomib, primarily at the higher doses tested and when given with agents where rash is an overlapping toxicity. The rash may range from limited erythematous areas, macular and/or small papular bumps that may or may not be pruritic over a few areas of the body, to a more generalized eruption that is predominately on the trunk or extremities. Rash has been most commonly characterized as maculopapular or macular. To date, when it does occur, rash is most commonly reported within the first 3 cycles of therapy. The rash is often transient, self-limiting, and is typically Grade 1 to 2 in severity.

Symptomatic measures such as antihistamines or corticosteroids (oral or topical) have been successfully used to manage rash and have been used prophylactically in subsequent cycles. The use of a topical, IV, or oral steroid (eg, prednisone \leq 10 mg per day or equivalent) is permitted. Management of a Grade 3 rash may require intravenous antihistamines or corticosteroids. Administration of ixazomib (and/or other causative agent if given in combination) should be modified per protocol and re-initiated at a reduced level from where rash was noted (also, per protocol).

In line with clinical practice, dermatology consult and biopsy of Grade 3 or higher rash or any SAE involving rash is recommended. Prophylactic measures should also be considered if a patient has previously developed a rash (eg, using a thick, alcohol-free emollient cream on dry areas of the body or oral or topical antihistamines). A rare risk is Stevens-Johnson Syndrome, a severe and potentially life-threatening rash with skin peeling and mouth sores, which should be managed symptomatically according to standard medical practice. Punch biopsies for histopathological analysis are encouraged at the discretion of the investigator.

CONFIDENTIAL

This document is confidential. Do not disclose or use except as authorized.

Thrombocytopenia

Blood counts should be monitored regularly as outlined in the protocol with additional testing obtained according to standard clinical practice. Thrombocytopenia may be severe but has been manageable with platelet transfusions according to standard clinical practice. Ixazomib administration should be modified as noted as per dose modification recommendations in the protocol when thrombocytopenia occurs (see Table 6-2). Therapy can be reinitiated at a reduced level upon recovery of platelet counts. A rare risk is thrombotic thrombocytopenic purpura (TTP), a rare blood disorder where blood clots form in small blood vessels throughout the body characterized by thrombocytopenia, petechiae, fever, or possibly more serious signs and symptoms. TTP should be managed symptomatically according to standard medical practice.

Neutropenia

Blood counts should be monitored regularly as outlined in the protocol with additional testing obtained according to standard clinical practice. Neutropenia may be severe but has been manageable. Growth factor support is not required but may be considered according to standard clinical practice. Ixazomib administration should be modified as noted as per dose modification recommendations in the protocol when neutropenia occurs (see Table 6-2). Therapy can be reinitiated at a reduced level upon recovery of ANC's.

Fluid Deficit

Dehydration should be avoided since ixazomib may cause vomiting, diarrhea, and dehydration. Acute renal failure has been reported in patients treated with ixazomib, commonly in the setting of the previously noted gastrointestinal toxicities and dehydration.

Fluid deficit should be corrected before initiation of study drug and as needed during treatment to avoid dehydration.

Hypotension

Symptomatic hypotension and orthostatic hypotension with or without syncope have been reported with ixazomib. Blood pressure should be closely monitored while the patient is on study treatment and fluid deficit should be corrected as needed, especially in the setting of concomitant symptoms such as nausea, vomiting, diarrhea, or anorexia. Patients taking medications and/or diuretics to manage their blood pressure (for either hypo- or hypertension)

CONFIDENTIAL

This document is confidential. Do not disclose or use except as authorized.

should be managed according to standard clinical practice, including considerations for dose adjustments of their concomitant medications during the course of the trial. Fluid deficit should be corrected before initiation of study drug and as needed during treatment to avoid dehydration.

Posterior Reversible Encephalopathy Syndrome

One case of posterior reversible encephalopathy syndrome, which ultimately resolved, has been reported with ixazomib. This condition is characterized by headache, seizures and visual loss, as well as abrupt increase in blood pressure. Diagnosis may be confirmed by magnetic resonance imaging (MRI). If the syndrome is diagnosed or suspected, symptom-directed treatment should be maintained until the condition is reversed by control of hypertension or other instigating factors.

Transverse Myelitis

Transverse myelitis has also been reported with ixazomib. It is not known if ixazomib causes transverse myelitis; however, because it happened to a patient receiving ixazomib, the possibility that ixazomib may have contributed to transverse myelitis cannot be excluded.

6.1.6 Adverse Event List for Rituximab

Anticipated Drug Toxicities

The following safety data on rituximab related adverse events has been compiled from 315 patients who were treated in 5 single agent studies.

Infusion Related Events

Rituximab is associated with hypersensitivity reactions, which may respond to adjustments in the infusion rate. An infusion related symptom complex consisting of fever and chills/rigors occurred in the majority of patients during the first rituximab infusion. Other frequent infusion related symptoms include nausea, urticaria, fatigue, headache, pruritus, bronchospasm, dyspnea, sensation of tongue or throat swelling (angioedema), rhinitis, vomiting, hypotension, flushing, and pain at disease sites. These reactions have generally occurred within 30 minutes to 2 hours of beginning the first infusion, and resolved with slowing or interruption of the rituximab infusion and with supportive care (IV saline, diphenhydramine, famotidine or cimetidine, acetaminophen, glucocorticoids). The incidence of infusion related events decreased from 80% (7% Grade 3/4) during the first infusion to approximately 40% (5% to 10% Grade 3/4) with subsequent infusions. Mild to moderate hypotension requiring interruption of rituximab infusion with or without administration of IV saline occurred in 10% of patients. Isolated occurrences of severe reactions requiring epinephrine have been reported in patients receiving rituximab for other indications. Angioedema was reported in 13% of patients, and was serious in one patient. Bronchospasm occurred in 8% of patients; one quarter of these patients were treated with bronchodilators. A single report of bronchiolitis obliterans was noted.

CONFIDENTIAL

This document is confidential. Do not disclose or use except as authorized.

Immunologic Events

Rituximab induced B-cell depletion in 70 to 80% of patients, and was associated with decreased serum immunoglobulins in a minority of patients. The incidence of infection does not appear to be increased. During the treatment period, 50 patients in the pivotal trial developed 68 infectious events; 6 (9%) were grade 3 in severity, and none were Grade 4 events. Of the 6 serious infectious events, none were associated with neutropenia. The serious bacterial events included sepsis due to *Listeria* (n=1), staphylococcal bacteremia (n=1), and polymicrobial sepsis (n=1). In the post-treatment period (30 days to 11 months following the last dose), bacterial infections included sepsis (n=1); significant viral infections included herpes simplex infections (n=2) and herpes zoster (n=3). The following immune serious adverse events have been reported to occur rarely (<0.1%) in patients following completion of rituximab infusions: arthritis, disorders of blood vessels (vasculitis, serum sickness and lupus-like syndrome), lung disorders including pleuritis and scarring of the lung (bronchiolitis obliterans), eye disorders (uveitis and optic neuritis), and severe bullous skin reactions (including toxic epidermal necrolysis and pemphigus) that may result in fatal outcomes. Patients may have these symptoms alone or in combination with rash and polyarthritis.

Hepatitis B virus (HBV) reactivation with fulminant hepatitis, hepatic failure, and death has been reported in some patients with hematologic malignancies treated with rituximab. The majority of patients received rituximab in combination with chemotherapy. The median time to the diagnosis of hepatitis was approximately 4 months after the initiation of rituximab and approximately one month after the last dose.

Retreatment Events

Twenty-one patients have received more than one course of rituximab. The percentage of patients reporting any adverse event upon retreatment was similar to the percentage of patients reporting adverse events upon initial exposure. The following events were reported more frequently in retreated participants: asthenia, throat irritation, flushing, tachycardia, anorexia, leukopenia, thrombocytopenia, anemia, peripheral edema, dizziness, depression, respiratory symptoms, night sweats and pruritus.

Hematologic Events

In clinical trials, Grade 3 and 4 cytopenias were reported in 48% of patients treated with rituximab including: lymphopenia (40%), neutropenia (6%), leukopenia (4%), anemia (3%), and thrombocytopenia (2%). The median duration of lymphopenia was 14 days (range, 1 to 588 days) and of neutropenia was 13 days (range, 2 to 116 days). A single occurrence of transient aplastic anemia (pure red cell aplasia) and two occurrences of hemolytic anemia following rituximab therapy were reported.

In addition, there have been a limited number of post marketing reports of prolonged pancytopenia, marrow hypoplasia, and late onset neutropenia (defined as occurring 40 days after the last dose of rituximab) in patients with hematologic malignancies. In reported cases of late

CONFIDENTIAL

This document is confidential. Do not disclose or use except as authorized.

onset neutropenia (NCI-CTC Grade 3 and 4), the median duration of neutropenia was 10 days (range 3 to 148 days). Documented resolution of the neutropenia was described in approximately one-half of the reported cases; of those with documented recovery, approximately half received growth factor support. In the remaining cases, information on resolution was not provided. More than half of the reported cases of delayed onset neutropenia occurred in patients who had undergone prior autologous bone marrow transplantation. In an adequately designed, controlled, clinical trial, the reported incidence of NCI-CTC Grade 3 and 4 neutropenia was higher in patients receiving rituximab in combination with fludarabine as compared to those receiving fludarabine alone (76% [39/51] vs. 39% [21/53]).

Cardiopulmonary Events

Patients with pre-existing cardiac conditions, including arrhythmia and angina have had recurrences of these cardiac events during rituximab infusions. Four patients developed arrhythmias during rituximab infusion. One of the four patients discontinued treatment because of ventricular tachycardia and supraventricular tachycardias. The other three patients experienced trigeminy (1) and irregular pulse (2) and did not require discontinuation of therapy. Angina was reported during infusion and myocardial infarction occurred 4 days post-infusion in one participant with a history of myocardial infarction. In rare cases, severe and fatal cardiopulmonary events, including hypoxia, pulmonary infiltrates, acute respiratory distress syndrome, myocardial infarction, and cardiogenic shock have occurred. Nearly all-fatal infusion-related events occurred in association with the first infusion.

Potential for fatal infusion reactions

In post marketing studies, rare events of tumor lysis syndrome have been reported in patients who had a high number of circulating malignant cells (>25,000/uI), with a rapid reduction in tumor volume, renal insufficiency, hyperkalemia, hypocalcemia, hyperuricemia, and hyperphosphatemia noted in these patients. For additional details, and updates see current rituximab package insert. In rare cases, severe and fatal cardiopulmonary events, including hypoxia, pulmonary infiltrates, acute respiratory distress syndrome, myocardial infarction, and cardiogenic shock, have occurred. Nearly all-fatal infusion-related events occurred in association with the first infusion.

Prevention and management of abrupt increases in serum IgM and viscosity following Rituximab use in patients with Waldenström's macroglobulinemia

Abrupt and paradoxical increases in IgM levels have been reported with the use of rituximab in patients with Waldenström's macroglobulinemia, which may aggravate hyperviscosity and contribute to hyperviscosity related symptoms. Plasmapheresis is strongly encouraged for those patients at increased risk for hyperviscosity. Rituximab will be omitted for Cycles 1 and 2 in all patients.

6.1.7 Adverse Event List for Dexamethasone

CONFIDENTIAL

This document is confidential. Do not disclose or use except as authorized.

Fluid and electrolyte disturbances: sodium retention; fluid retention; congestive heart failure in susceptible patients; potassium loss; hypokalemic alkalosis; hypertension; hypotension or shock-like reaction.

Musculoskeletal: muscle weakness; steroid myopathy; loss of muscle mass; osteoporosis; vertebral compression fractures; aseptic necrosis of femoral and humeral heads; pathologic fracture of long bones; tendon rupture.

Gastrointestinal: peptic ulcer with possible subsequent perforation and hemorrhage; perforation of the small and large bowel, particularly in patients with inflammatory bowel disease; pancreatitis; abdominal distention; ulcerative esophagitis.

Dermatologic: impaired wound healing; thin fragile skin; petechiae and ecchymoses; erythema; increased sweating; may suppress reactions to skin tests, burning or tingling, especially in the perineal area (after i.v. injection), other cutaneous reactions such as allergic dermatitis, urticaria, angioneurotic edema.

Neurological: convulsions; increased intracranial pressure with papilledema (pseudotumor cerebri) usually after treatment; vertigo; headache; psychic disturbances.

Endocrine: menstrual irregularities; development of cushingoid state; suppression of growth in children; secondary adrenocortical and pituitary unresponsiveness, particularly in times of stress, as in trauma, surgery or illness; decreased carbohydrate tolerance; manifestations of latent diabetes mellitus; increased requirements for insulin or oral hypoglycemic agents in diabetes; hirsutism.

Ophthalmic: posterior subcapsular cataracts; increased intraocular pressure; glaucoma; exophthalmos; retinopathy of prematurity.

Cardiovascular: myocardial rupture following recent myocardial infarction; hypertrophic cardiomyopathy in low birth weight infants.

Metabolic: negative nitrogen balance due to protein catabolism.

Other: anaphylactoid or hypersensitivity reactions, thromboembolism, weight gain, increased appetite, nausea, malaise, hiccups.

The following additional adverse reactions are related to parenteral corticosteroid therapy: rare instances of blindness associated with intralesional therapy around the face and head; hyperpigmentation or hypopigmentation; subcutaneous and cutaneous atrophy; sterile abscess; post-injection flare (following intra-articular use); Charcot-like arthropathy.

6.2 Toxicity Management and Dose Modifications/Delays

6.2.1 Ixazomib

CONFIDENTIAL

This document is confidential. Do not disclose or use except as authorized.

Treatment with **ixazomib** will use a cycle length of 28 days during induction and 8 weeks during maintenance. For a new cycle of treatment to begin, the patient must meet the following criteria:

- ANC must be $\geq 1,000/\text{mm}^3$.
- Platelet count must be $\geq 75,000/\text{mm}^3$.
- All other non-hematologic toxicity (except for alopecia) must have resolved to \leq Grade 1 or to the patient's baseline condition

Transfusion of blood products and G-CSF administration is not permissible on treatment days to meet the above requirements. If the patient fails to meet the above-cited criteria for initiation of the next cycle of treatment, dosing of ixazomib, rituximab, and dexamethasone should be delayed for 1 week. At the end of that time, the patient should be re-evaluated to determine whether the criteria have been met. If the patient continues to fail to meet the above-cited criteria, delay therapy and continue to re evaluate. The maximum delay before treatment should be discontinued will be 28 days or at the discretion of the Principal Investigator.

For dosing recommendations upon recovery, refer to Table 6-2 and Table 6-3.

Table 6-1 MLN908 Dose Adjustments

Dose Level	Dose (mg)
Starting Dose	4.0 mg
-1	3.0 mg
-2	2.3 mg
-3	Discontinue

6.2.1.1 Dose Reductions for Hematologic Toxicities

Dosage adjustments for hematologic toxicity are outlined in Table 6-2.

**Table 6-2 Ixazomib Dose Adjustments for Hematologic Toxicities
Ixazomib can be held for maximum of 28 days except at discretion of PI**

Criteria	Action
Within-Cycle Dose Modifications	
If platelet count $\leq 30 \times 10^9/\text{L}$ or ANC $\leq 0.50 \times 10^9/\text{L}$ on a ixazomib dosing day (other than Day 1)	Ixazomib dose should be withheld. Complete blood count (CBC) with differential should be repeated at least every other day until the ANC and/or platelet counts have exceeded the prespecified values (see Section 6.2.1) on at least 2 occasions. Upon recovery, ixazomib may be reinitiated with 1 dose level reduction.

CONFIDENTIAL

This document is confidential. Do not disclose or use except as authorized.

Dosage adjustments for hematologic toxicity are outlined in Table 6-2.

Table 6-2 Ixazomib Dose Adjustments for Hematologic Toxicities
Ixazomib can be held for maximum of 28 days except at discretion of PI

Criteria	Action
Dose Modifications for Subsequent Treatment Cycles	
Delay of > 2 weeks in the start of a subsequent cycle due to lack of toxicity recovery as defined in Section 6.3.1.	Hold ixazomib until resolution as per criteria Section 6.2. Upon recovery, reduce ixazomib 1 dose level.
ANC < 1.0 × 10 ⁹ /L, platelet count < 75 × 10 ⁹ /L, or other nonhematologic toxicities > Grade 1 or not to the patient’s baseline condition	The maximum delay before treatment should be discontinued will be 28 days or at the discretion of the PI.
Dose Modifications for Subsequent Treatment Cycles	
All hematologic toxicities	For hematologic toxicity that occurs during a cycle but recover in time for the start of the next cycle,: If dose was reduced within the cycle, start the next cycle at that same dose. If due to toxicity timing, ie, after Day 15 dosing thus a dose reduction was not required at that point in the cycle, reduce ixazomib by 1 dose level at the start of that cycle. Do not reduce the dose both within a cycle and at the start of the cycle for the same most severe toxicity.

6.2.1.2Dose Reductions for Non-Hematologic Toxicities

CONFIDENTIAL

This document is confidential. Do not disclose or use except as authorized.

Table 6-3 Ixazomib Treatment Modification (Delays, Reductions, and Discontinuations) Due to Adverse Events (Non-Hematologic Toxicities)

Ixazomib can be held for maximum of 28 days except at discretion of PI

Adverse Event (Severity)	Action on Study Drug	Further Considerations
Peripheral Neuropathy:		
Grade 1 peripheral neuropathy	
 No action 	Grade 1 signs and symptoms: asymptomatic; without pain or loss of function; clinical or diagnostic observations only [14]
New or worsening Grade 1 peripheral neuropathy with pain or Grade 2	
 Hold study drug until resolution to Grade \leq 1 or baseline 	Grade 2 signs and symptoms: Moderate symptoms; limiting instrumental activities of daily living (ADL) [14]
New or worsening Grade 2 peripheral neuropathy with pain or Grade 3	
 Hold study drug until resolution to Grade \leq 1 or baseline Reduce study drug to next lower dose upon recovery 	Grade 3 signs and symptoms: severe symptoms; limiting self-care ADL; assistive device indicated [14]
New or worsening Grade 4 peripheral neuropathy	
 Discontinue study drug 	
Grade 2 Rash	
 Symptomatic recommendations as per section 6.6 	The investigator and project clinician may discuss considerations for dose modifications and symptom management.
Grade 3 nonhematologic toxicity judged to be related to study drug	
 Hold study drug until resolution to Grade $<$ 1 or baseline 	Symptomatic recommendations noted in Section 6.6
If not recovered to $<$ Grade 1 or baseline within 4 weeks	
 Reduce study drug 1 to next lower dose upon return to $<$ Grade 1 or baseline 	
Subsequent recurrence Grade 3 that does not recover to $<$ Grade 1 or baseline within 4 weeks	
 Hold study drug until resolution to Grade $<$ 1 or baseline Reduce study drug to next lower dose 	Monitor closely, take appropriate medical precautions, and provide appropriate symptomatic care

CONFIDENTIAL

This document is confidential. Do not disclose or use except as authorized.

Table 6-3 Ixazomib Treatment Modification (Delays, Reductions, and Discontinuations) Due to Adverse Events (Non-Hematologic Toxicities)

Ixazomib can be held for maximum of 28 days except at discretion of PI

Adverse Event (Severity)	Action on Study Drug	Further Considerations
Grade 4 nonhematologic toxicities judged to be related to study drug	
 Consider permanently discontinuing study drug 	Exceptions are cases in which the investigator determines the patient is obtaining a clinical benefit

Once ixazomib is reduced for any toxicity, the dose may not be re-escalated.

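### For related Grade 3 non-haematologic toxicity other than neuropathy, Tables 6-2 and 6-3 and Sections 6.2.1 and 6.1.5 conflict on when ixazomib is held, reduced or restarted

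*Combined protocol and SAP*

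**What the plan says.** **Table 6-3 (Section 6.2.1.2).** For a related Grade 3 non-haematologic event the action is "Hold study drug until resolution to Grade $<$ 1 or baseline"; that row gives no restart dose. The next row applies on the condition "If not recovered to $<$ Grade 1 or baseline within 4 weeks", with the action "Reduce study drug 1 to next lower dose upon return to $<$ Grade 1 or baseline". The recurrence row carries the same time condition: "Subsequent recurrence Grade 3 that does not recover to $<$ Grade 1 or baseline within 4 weeks". The table's header, which also stands over Table 6-2, reads "Ixazomib can be held for maximum of 28 days except at discretion of PI".

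**Section 6.2.1.** To start a new cycle, non-haematologic toxicity "must have resolved to \leq Grade 1" or returned to baseline. If it has not, the cycle is delayed, and "The maximum delay before treatment should be discontinued will be 28 days or at the discretion of the Principal Investigator". For dosing after recovery the reader is sent to both Table 6-2 and Table 6-3.

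**Table 6-2 (Section 6.2.1.1, dose adjustments; not the rash table that has the same number in Section 6.1.1).** If the start of a cycle is delayed by more than 2 weeks because toxicity has not recovered, ixazomib comes down one dose level. The adjoining criteria name non-haematologic toxicity above Grade 1.

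**Section 6.1.5.** Directly after discussing Grade 3 rash, it says that ixazomib should be "re-initiated at a reduced level from where rash was noted (also, per protocol").

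**Neuropathy rows of Table 6-3.** Recovery here is Grade 1 or lower, or baseline. For Grade 3, the dose is reduced on recovery with no time condition.

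A note after Table 6-3 adds that a reduced dose may not be raised again.

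**The concern.** An investigator needs three answers after a related Grade 3 event: when it counts as recovered, what dose to restart at, and when the hold has lasted too long. The protocol answers each in more than one place, and the answers differ. The trigger for reducing is as long as the limit on holding. A second table has a shorter trigger. The rash guidance defers to a protocol rule that the table does not contain for prompt recovery.

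Toxicity is a primary objective (Section 1.2). Exposure is summarised under Section 14.5, and events leading to discontinuation are tabulated under Section 14.6. If investigators resolve the conflict differently, those summaries partly reflect local reading as well as drug tolerability. Because reductions cannot be reversed, a single reading affects all later cycles of that patient.

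**Working it through.** The plan gives no figure to reproduce. The check compares the time limits and sets the passages side by side.

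**1. Length of the two periods.** 4 weeks × 7 = 28 days, equal to the limit on holding.

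**2. Days between the reduction trigger and the limit.** Let *o* be the day of onset and *s* the day on which the 28-day limit starts to run. Counting the 4 weeks from onset, the trigger falls on day *o* + 28 and the limit on day *s* + 28. The gap is (*s* + 28) − (*o* + 28) = *s* − *o*.

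Inputs: doses on days 1, 8 and 15; next cycle due on day 29 in induction (28-day cycle) and day 57 in maintenance (8 × 7 = 56 days). Assumptions: onset lies between days 1 and 28, and an event on a dosing day begins after that day's dose.

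| Limit runs from | Gap in induction, days | Gap in maintenance, days |
|---|---|---|
| Same start as the 4 weeks | 0 | 0 |
| First withheld dose | 1 (onset day 14: 15 − 14) to 14 (onset day 15: 29 − 15) | 1 (onset day 14: 15 − 14) to 42 (onset day 15: 57 − 15) |
| Due date of next cycle | 1 (29 − 28) to 28 (29 − 1) | 29 (57 − 28) to 56 (57 − 1) |

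In maintenance, an event on day 15 reaches its 4-week point on day 43, before any dose is due on day 57. The documents do not say which line of the table is meant.

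**3. Table 6-2 against Table 6-3.** Take onset on induction day 20 and recovery on day 45. The event lasted 45 − 20 = 25 days, which is less than 28, so the reduction row of Table 6-3 is not met. The next cycle was due on day 29, so it is at least 45 − 29 = 16 days late. That exceeds 14 days, and Table 6-2 reduces one level. Counting the 4 weeks from day 29 instead gives 16 days, still below 28. In this example the conflict does not depend on the clock start.

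**4. Section 6.1.5 against Table 6-3.** For Grade 3 rash that clears fully within 4 weeks, Section 6.1.5 expects a reduced restart. Table 6-3 states no reduction.

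**5. Recovery threshold.** Suppose a Grade 3 rash has fallen to Grade 1 on day 20 of the hold in a patient with no rash at baseline. Section 6.2.1 treats the rash as recovered for a new cycle. Table 6-3, as printed, keeps the hold because Grade 1 is not below Grade 1. Section 6.1.5 points to a reduced restart. If rash was already Grade 1 at baseline, the baseline clause satisfies both thresholds, so this conflict is confined to residual Grade 1 above baseline.

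**6. Weight of one patient.** Section 14.1 reports 27 accrued, of whom one never started: 27 − 1 = 26 treated. One patient is 1/26 = 3.8 percentage points.

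**The case against.** The strongest reply is that the periods measure different things. The 4 weeks concern recovery of the event, the table header concerns how long drug is withheld, and Section 6.2.1 concerns lateness of a cycle. Every form of the limit also allows an exception at the principal investigator's discretion, so the reduction row can be read as giving the restart dose after a permitted longer hold. This largely stands, and it rules out three stronger readings that a reader might infer:

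- **That the reduction row can be reached only by discretion.** This holds only if the two periods start together, which the documents do not say. On the other starts in the table above, at least 1 day remains.
- **That any patient unrecovered at 28 days must stop.** The wording about stopping stands in Section 6.2.1 and Table 6-2 and concerns delay of a cycle. The header of Table 6-3 limits the hold and does not mention stopping.
- **That no patient who recovers within 28 days has a reduction rule.** Table 6-2 can reduce earlier, after a cycle delay of more than 2 weeks.

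One may answer that Table 6-2 is titled for haematologic toxicity. But Section 6.2.1 refers to both tables, and the adjoining criteria in Table 6-2 include non-haematologic events. The cross-references do not settle it: the tables point to Sections 6.3.1 and 6.6, while Section 6 ends at 6.2.

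The threshold sign may be an error of text extraction, although the less-than-or-equal sign was read correctly in the neuropathy rows of the same table. It needs a look at the source PDF.

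Finally, accrual is reported as complete, and removal reasons, treatment forms and total drug taken are already collected. New wording may therefore change little dosing, but those records do not by themselves show which rule was followed.

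**Conclusion.** The dosing rules conflict for related Grade 3 non-haematologic toxicity other than neuropathy, and this should be corrected. Two conflicts do not rest on the undefined clock starts: the 2-week trigger in Table 6-2 against the 4-week trigger in Table 6-3, and the rash sentence in Section 6.1.5 against Table 6-3. The first assumes that Table 6-2 covers non-haematologic delays, as Section 6.2.1 and the adjoining criteria indicate. The threshold conflict is conditional on the printed sign being right. The equality of 4 weeks and 28 days is a real ambiguity: the gap is 0 days on a common start and 1 to 56 days on the other starts examined, for onset on days 1 to 28.

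Discretion permits departures but does not tell sites which default they depart from. The number of patients affected is not in the documents. Each one carries 3.8 percentage points in any proportion of the 26 treated. No effect on the recorded incidence of adverse events has been shown; the exposure, reduction and discontinuation summaries are the ones most directly exposed.

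**What to change.** The sponsor should reconcile Table 6-3 and its header, Table 6-2, Section 6.2.1 and Section 6.1.5, so that together they state:

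- one recovery threshold, after checking the printed sign against the source PDF;
- one trigger for dose reduction, including how it applies to rash and to delayed cycles;
- a defined start for the 4-week period and for the 28-day period, and how the two interact.

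Which threshold, trigger or start is right is a clinical decision for the sponsor, and no view is taken here. The references to Sections 6.3.1 and 6.6 should be corrected at the same time.

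Each use of the principal investigator's discretion to extend a hold or delay should be recorded and listed with the safety results, including for patients already treated, with the rule followed and the restart dose. The cost is protocol wording, plus one listing that may need a look back at treatment records. Sample size and the primary efficacy analysis are unchanged.
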